9.4.3. CRITERIA FOR NONLOCAL FAILURE

9.4.3.1. DISTANT FAILURE (includes regional failure): documented if clinical, bone scan, CT or other imaging study shows metastatic disease. Biochemical failure with a negative prostate biopsy shall be considered distant only failure. Biopsy of metastatic site required if radiographic or clinical findings are equivocal. Type of metastatic failure (distant and/or regional) shall be recorded if known. Prostate biopsy recommended at this time.

9.4.3.2. DISEASE-FREE SURVIVAL: for any measure of disease, including PE, PSA, bone scan, CT/MRI and biopsy, or death.

9.4.3.3. DISEASE-SPECIFIC SURVIVAL: for any of the following:

9.4.3.3.1. Death due to prostate cancer.

9.4.3.3.2. Death due to other causes, with active malignancy (defined by clinical or biochemical evidence of progression). If a patient suffered a previous relapse, but has inactive disease, this is not considered a disease-specific death.

9.4.3.3.3. Death due to complications of treatment.

9.4.3.4. OVERALL SURVIVAL: Survival duration will be measured from the date of study entry to the date of death from any cause

10. DATA COLLECTION

See appendix IV for Case Report Forms & patient questionnaires.

11. STATISTICAL CONSIDERATIONS

11.1. DATA ANALYSIS AND SAMPLE SIZE CALCULATION

Response rates with 95% confidence intervals and one-sample Kaplan-Meier analysis will be performed to show 5 year disease free survival and overall survival for patients treated with CyberKnife® SBRT monotherapy and patients treated with whole pelvis IMRT and ADT per current standards of care, followed by CyberKnife® SBRT boost.

In treatment groups, toxicity, rates of local failure, distant failure, clinical disease-free survival, disease-specific survival, and overall survival; quality of life (QOL) in generic and organ-specific domains will be reported descriptively for the samples. In addition descriptive statistics will be provided comparing the CyberKnife® Stereotactic Radiosurgery System bDFS rate to published HDR monotherapy bDFS rates reported in the literature for each group.

Investigators expect that overall, patients treated with CyberKnife® SBRT monotherapy will have a 5 year PSA DFS rate of $80\% \pm 0.15$ (total width = .30) using a confidence level of 95%, a required sample size of 32 subjects is necessary.

Investigators expect that overall, patients treated with whole pelvis IMRT and ADT per current standards of care, followed by CyberKnife® SBRT boost will have a 5 year PSA DFS rate of $70\% \pm 0.15$ (total width = .30) using a confidence level of 95%, a required sample size of 40 subjects is necessary.

It is expected that up to 150 subjects will be enrolled at this site.

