1.12. The feasibility of CyberKnife® for treating localized prostate cancer was first described by King at Stanford University. Their phase I protocol delivered 36.25Gy in 5 fractions of 7.25Gy. In a recent report of acute and 18-month late toxicity in 26 “low-risk” patients, no patient experienced grade 3 or 4 acute or late toxicity, and only one patient experienced a grade 2 late morbidity (urethral stricture). Toxicity was less than that reported in MD Anderson’s external beam dose escalation trial. Mean PSA 18 months after treatment was 0.22ng/m²⁵. Similar excellent results have also been reported by Jabbari et al. from the University of California for both CyberKnife® monotherapy and boost post whole pelvic radiation therapy³, and King and Freedman using the original Stanford fractionation of five fractions when used as monotherapy⁴.

1.13. Another potential benefit of CyberKnife® radiosurgery relative to HDR brachytherapy is better preservation of potency, even if the radiation distribution is essentially identical between these modalities. This is so because needle trauma has been identified as a potentially significant contributory factor to erectile dysfunction with brachytherapy, including HDR-based monotherapy technique, presumably due to direct physical injury to the neurovascular bundle and/or bulb of the penis, particularly when greater than 13 needle insertions are performed.²⁷ By comparison, CyberKnife® radiosurgery is noninvasive, and so removes this particular erectile dysfunction risk factor.

Table 1. 5-Year bDFS Outcomes for HDR-Monotherapy for Prostate Cancer

HDR Details	Institution	#pts	Median f/u yrs	Phoenix	ASTRO
6–7.25 Gy x 6	CA Endocurie ³⁰	117	3.3		97%
9.5 Gy x 4	Beaumont ³¹	95	4.2		98%
7.5 Gy x 6	Texas Tech ³²	145	5		90%
6.5 Gy x 6	Gamma West – Fav. (SLC) ³³	209	1.2	96%*	99%*
	Gamma West – Int. ³³	119	1.2	89%*	89%*
6 Gy x 8-9	Osaka (Japan) ³⁴	111	2.25		70%†
Totals		796	2.4		90%

*3 year result; Projecting constant failure rate in this series to 5 years yields 98% and 82% ASTRO-definition PSA DFS for favorable and intermediate risk cases, respectively. †Predominantly unfavorable prognosis cases in this series; 5 year local control is 97%.

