Based on the data provided in the reports summarized above, and adding a PSA DFS degradation factor to the Gamma West series to compensate for their short median follow-up, the average calculated 5 year HDR monotherapy ASTRO-based PSA DFS is 98% for favorable prognosis, 82% for intermediate prognosis and 59% for unfavorable prognosis cases. There are too few Phoenix-based PSA DFS results to project a meaningful Phoenix-based HDR monotherapy PSA DFS efficacy result.

It is anticipated that the case mix in this study will be approximately 75% intermediate, and 25% high risk prognosis cases, leading to a predicted 5 year PSA DFS rate of 85%-90% for intermediate risk patients, and 75%-80% for high risk patients based on HDR brachytherapy boost trial. **Table 2. Toxicity review for HDR-Monotherapy for Prostate Cancer**

HDR Details	Institution	# pts	Median f/u	>= Gd 3 toxicity		
				Total (%)	GI (%)	GU (%)
6-7.25Gy x 6	CA Endocurie ³⁰	117	3.3	3	0	3
9.5Gy x 4	Beaumont ³¹	95	4.2	8	0	8
7.5Gy x 6	Texas Tech ³²	145	5	5 – 8*	1	4 – 7*
6.5Gy x 6	Gamma West (SLC) ³³	328	1.2	1	0	1
6Gy x 8-9	Osaka (Japan) ³⁴	111	2.25	7	1	6
Totals		796	2.4	6	0 -1	5

*3% acute and 4% chronic grade 3 GU toxicity – It is unclear to what degree acute and chronic grade 3 GU toxicity populations overlap in this study.

To confirm our hypothesis that CyberKnife® radiosurgery may be made to resemble a “noninvasive HDR dosimetry delivery system,” in addition to simply creating equivalent dosimetry, it is necessary to show clinical equivalence both in terms of efficacy and toxicity. Due to short median follow-up, the incidence of >= grade 3 late toxicity is likely underestimated. We project that the incidence of late toxicity will increase by approximately 50% when all data reach 5 years maturity, yielding a projected cumulative 5 year HDR monotherapy grade 3 toxicity incidence of 9% (7-8% GU; 1-2% GI). In this study, biochemical disease-free survival (ASTRO and Phoenix definition), freedom from local recurrence, freedom from distant relapse, clinical disease-free survival, disease-specific survival and overall survival will be recorded. The incidence of grade 3 or higher toxicity and the effect of CyberKnife® radiosurgery on bladder, bowel, and sexual function will be followed and monitored using standardized, patient self-administered questionnaires²⁸ and compared with results published in peer-reviewed literature for other prostate cancer therapeutic modalities.²⁹

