2. OBJECTIVES

PRIMARY OBJECTIVES:

- Document the efficacy of the CyberKnife® procedure, where efficacy is defined by biochemical Disease-Free Survival (bDFS), using Phoenix and ASTRO definitions, at 5 years.

- Compare the CyberKnife® Stereotactic Radiosurgery System bDFS rate to published HDR monotherapy bDFS rates reported in the literature.

SECONDARY OBJECTIVES:

- Measure rates of acute and late grade 3-5 gastrointestinal and genitourinary toxicity observed during the five years following CyberKnife® Stereotactic Radiosurgery System for prostate cancer. Acute toxicity will be defined as occurring within 90 days from completion of treatment. Late toxicity will be defined as occurring more than 90 days from completion of treatment. It is graded based upon Common Terminology Criteria for Adverse Events (CTCAE), v3.0 and RTOG/ECOG definitions (see appendix 5).
- Measure rates of local failure, distant failure, clinical disease-free survival, disease-specific survival, and overall survival
- Examine Quality of Life (QOL) in generic and organ-specific domains

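### Boost patients also receive IMRT, yet their bDFS is compared only with published HDR monotherapy rates, so for them the comparison does not isolate CyberKnife versus HDR

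*Combined protocol and SAP*

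**What the plan says.** The second primary objective in Section 2 reads "Compare the CyberKnife® Stereotactic Radiosurgery System bDFS rate to published HDR monotherapy bDFS rates reported in the literature". It does not separate monotherapy from boost patients. Section 11.1 defines two treatment groups, CyberKnife monotherapy and IMRT with ADT plus CyberKnife boost, and plans descriptive statistics "comparing the CyberKnife® Stereotactic Radiosurgery System bDFS rate to published HDR monotherapy bDFS rates reported in the literature for each group".

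Section 8.1 gives high-risk patients one option: a 21 Gy boost with whole pelvis IMRT of 45-50.4 Gy. Intermediate-risk patients receive either CyberKnife monotherapy or the boost with prostate/seminal vesicle IMRT of 45-50.4 Gy. ADT is strongly recommended for both risk groups, and for intermediate risk this includes the monotherapy patients.

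The purpose is stated in Section 1: to confirm that CyberKnife can act as a noninvasive form of HDR, "it is necessary to show clinical equivalence both in terms of efficacy and toxicity". The same section gives average 5-year HDR monotherapy rates (ASTRO definition) of "98% for favorable prognosis, 82% for intermediate prognosis and 59% for unfavorable prognosis cases". It then gives, for this trial, a "predicted 5 year PSA DFS rate of 85%-90% for intermediate risk patients, and 75%-80% for high risk patients based on HDR brachytherapy boost trial". No passage names an HDR boost comparator for the boost patients or restricts the HDR monotherapy comparison to monotherapy patients.

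**The concern.** A comparison with published series informs the CyberKnife-versus-HDR question only if the rest of the treatment is similar. For boost patients it is not: they have a full course of IMRT that HDR monotherapy patients, by definition, did not have. Boost patients could therefore look better than HDR because of the IMRT, and the result would be reported under a primary objective as if it described the device.

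ADT adds a second uncertainty. Section 8.1 itself credits short-term ADT with a survival benefit, but the documents do not say how much ADT was used in the HDR monotherapy series. This affects the monotherapy comparison as well as the boost comparison. Only the IMRT difference is both certain and confined to boost patients.

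**Working it through.** **Inputs**
- HDR monotherapy, 5-year, ASTRO: 82% intermediate, 59% unfavourable (Section 1, text after Table 1).
- Prediction for this trial from HDR boost data, failure definition not stated: 75-80% high risk (same place).
- Section 11.1: expected 5-year PSA DFS of 80% with n = 32 (monotherapy) and 70% with n = 40 (boost), for a 95% interval of total width 0.30.

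**1. The plan's own figures.** Take the smallest n for which the exact (Clopper-Pearson) 95% interval is no wider than 0.30. With x = n × p, the limits are Beta(0.025; x, n − x + 1) and Beta(0.975; x + 1, n − x).
- p = 0.80: n = 32, width 0.2985.
- p = 0.70: n = 40, width 0.2997.

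Both stated sizes reproduce. They depend only on the expected rate and the width, so the choice of comparator does not enter.

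The 82% also reproduces. The Table 1 footnote says "Projecting constant failure rate in this series to 5 years yields 98% and 82% ASTRO-definition PSA DFS" for favourable and intermediate cases. From the 3-year 89% in 119 patients, 0.89^(5/3) = 0.823. It is a projection from a series with 1.2 years median follow-up.

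**2. Treatments side by side**

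| Patients | Trial treatment | Planned comparator | Certain difference besides CyberKnife vs HDR |
|---|---|---|---|
| Intermediate, monotherapy | CyberKnife; ADT recommended | HDR monotherapy | None certain; ADT unknown |
| Intermediate, boost | CyberKnife + IMRT; ADT recommended | HDR monotherapy | IMRT |
| High risk (boost only) | CyberKnife + IMRT; ADT recommended | HDR monotherapy | IMRT |

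**3. Size if CyberKnife boost equals HDR boost.** Suppose high-risk patients do exactly as predicted from HDR boost data. Against 59% the apparent gains are 75 − 59 = 16 and 80 − 59 = 21 points, although CyberKnife has no advantage over HDR in this scenario.

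**4. The 70% in Section 11.1.** That section describes the group as having whole pelvis IMRT, which Section 8.1 gives only to high-risk patients. If 70% is therefore a high-risk figure:
- against HDR monotherapy: 70 − 59 = +11 points;
- against the HDR-boost-based prediction: 70 − 75 = −5 and 70 − 80 = −10 points.

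On that reading the sign depends on the comparator. At 28/40 the exact 95% interval is 53.5% to 83.4%, which covers 59% as well as 75-80%. The planned size would not settle the matter.

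**5. Sensitivity to the 59%.** This figure cannot be traced to a row of Table 1. The one series there marked as predominantly unfavourable (111 patients) shows 70%. Against 70%, step 3 gives 75 − 70 = 5 and 80 − 70 = 10 points, and the gap in step 4 against HDR monotherapy is zero. The gap shrinks, but the treatment difference remains.

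**The case against.** The strongest reply is that the comparison is descriptive. It has no test, margin or decision rule, and the first primary objective, the 5-year bDFS itself, does not depend on it. That stands, and it limits the matter to interpretation. It does not remove it, because the comparison is still a primary objective tied to a stated hypothesis of equivalence with HDR.

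One could also read each group as each risk group. This does not help: high-risk patients have only the boost option.

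Nor does the plan lack benchmarks. Section 9.4.1 keeps both failure definitions for literature comparison, and Section 1 gives ASTRO averages by prognosis while conceding "There are too few Phoenix-based PSA DFS results to project a meaningful Phoenix-based HDR monotherapy PSA DFS efficacy result". The trouble is the modality of the comparator.

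The point gaps are fairly criticised. The 75-80% is the plan's prediction, not a published rate, its failure definition is not given, and the 59% is of uncertain origin. The gaps are illustrative and are not estimates of an IMRT or ADT effect.

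A reader might infer three stronger things that the documents do not support:
- **That the sign also reverses for the whole boost group, more clearly with more patients.** This would set a mixed-risk group against high-risk figures. Assume 150 enrolled, 32 on monotherapy and the planned mix of "approximately 75% intermediate, and 25% high risk prognosis cases". That gives 118 boost patients: 0.25 × 150 = 37.5 high risk and 80.5 intermediate. The weighted HDR monotherapy figure is (37.5 × 59 + 80.5 × 82)/118 = 74.7%. The weighted prediction runs from (37.5 × 75 + 80.5 × 85)/118 = 81.8% to (37.5 × 80 + 80.5 × 90)/118 = 86.8%. A result of 70% lies below both.
- **That intermediate-risk boost patients carry a similar gap, 82% against 85-90%.** The 85-90% covers all intermediate-risk patients, including those on monotherapy, so it is not a boost figure.
- **That the monotherapy comparison is clean.** ADT is strongly recommended there too.

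**Conclusion.** The concern holds as a matter of interpretation. Followed as written, Sections 2 and 11.1 produce for every boost patient a comparison in which the IMRT effect cannot be separated from CyberKnife versus HDR. ADT may confound both this and the monotherapy comparison, to a degree the documents do not allow one to state.

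On the plan's own figures the distortion for high-risk patients could be 16 to 21 points, or 5 to 10 points if the 70% in Table 1 replaces the 59%. This assumes that the HDR-boost-based prediction is accurate and that differences in series, risk mix and failure definition are set aside. The change of sign at 70% holds only against 59%, and only if 70% refers to high-risk patients. The 5-year bDFS estimates and n = 32 and 40 do not change. The change should be made, but the trial's main estimates do not depend on it.

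**What to change.** In Sections 2 and 11.1:
- **(a)** Limit the HDR monotherapy comparison to CyberKnife monotherapy patients, using intermediate-risk rates, and note that the plan's 82% is projected to 5 years from a 3-year result.
- **(b)** Compare boost patients with published EBRT-plus-HDR-boost series, by risk group and with the same failure definition where available. If no matching published rate exists, report the boost bDFS without a comparison.
- **(c)** State ADT use for both trial groups and for every comparator series.

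Section 11.1 also has to be reconciled with Section 8.1 on which boost patients its 70% group contains, since it mentions only whole pelvis IMRT.

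By title, references 12, 15, 20, 22, 23 and 24 are boost sources and make a starting list. Their content must be checked: 23 and 24 are titled as initial or preliminary results and may not give 5-year rates. The 93% in Section 1.8 has no risk split or failure definition, so it cannot serve as it stands.

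The cost is a rewording of one objective and one analysis sentence, plus a short literature extraction. Sample sizes stay as they are. The downsides are that the boost series may be heterogeneous and that the high-risk contrast will probably look less favourable than it does against 59%.

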12 RISK TO BENEFIT RATIO

12.1 The determination of entry into the clinical evaluation will be made independent of the decision to treat with stereotactic radiosurgery. The radiation oncologist and/or medical team performing the procedure will discuss the potential risks associated with stereotactic radiosurgery and the potential benefits of control of disease progression, despite the limited clinical experience.

12.1Risks:

12.1.1. Risk classifications assigned below are based on currently available literature on treating prostate cancer with radiation therapy in a manner comparable to the radiosurgery planned for this protocol. The protocol for this clinical evaluation was designed to assure that the benefits and knowledge collected for stereotactic radiosurgery of malignant prostate tumors outweigh the potential risks to the subjects.

12.1.2. Risks to patients in this study include all those risks currently associated with fiducial placement as well as the risks of localizing and delivering radiation to the prostate environment. The safety of the CyberKnife® system in treating intracranial tumors has been well documented. Risks of the procedure for this clinical study along with the methods to minimize the risk are described below. The radiation risks presented are categorized according to version 2.0 of the National Cancer Institute's Common Toxicity Criteria. Likely effects are listed as those side effects which occur in more than 20% of patients. Less likely effects occur in 20% or less of patients treated. Rare but serious effects occur in less than 3% of patients.

12.1Risks Associated with External Radiation Therapy:

12.1.3. All patients treated under this protocol will be provided with specific instructions and contact information, in the event any patient develops side

effects. Many of these side effects go away shortly after radiation therapy is stopped, but in some cases side effects can be long-lasting or permanent.

The following includes risks associated with external beam radiation therapy to the prostate and surrounding pelvis.

Temporary fatigue (Likely): self-limited side effect.

Temporary frequent or loose stools (likely): see notes 1 & 3. Diet changes or Imodium will be prescribed if necessary.

Temporary urinary frequency, irritation, or reduced stream (Likely): see notes 1,2,3. Alpha blocker, antispasmodic, anti-inflammatory or other appropriate symptomatic medicines will be prescribed if necessary.

Temporary redness, tanning, or hair loss of skin in the treatment area (less likely): see note 1. Topical preparations will be prescribed, if necessary.

Permanent urinary “bother”, e.g. need to urinate urgently or frequently (less likely): see notes 1,2,3. Chronic alpha blocker or other medical therapy may be required.

Permanent bowel “bother”, e.g. need to move bowels urgently or frequently (less likely): see notes 1,2,3. Addition of “bulk” (e.g. Metamucil) to diet, or Imodium, may be required.

Rectal bleeding (rare, but serious): see notes 1,2,3. Hydrocortisone suppositories or enemas may be required; blood transfusions, photocoagulation, topical chemical coagulation, hyperbaric oxygen treatments. In extremely rare cases, colostomy may be necessary.

Urinary obstruction which could require catheter placement (Rare): see notes 2,3. Foley catheter, intermittent straight catheterization, or suprapubic catheter may be required.

Urethral scarring, which could impair urine stream, and could require surgery to repair (Rare, but serious): see notes 2,3. Cystoscopy, trans-urethra incision, and/or dilation may be required.

Leakage of small amounts of urine, which could require wearing pads in underwear (less likely): see notes 2,3.

Permanent inability to control urine, which could require a catheter, penile clamp, or surgery to repair (rare, but serious): see notes 2,3.

Urinary bleeding (rare, but serious): see notes 1,2,3: cystoscopy or electrocoagulation may be required. In extremely rare cases major surgery such as urinary diversion could be required.

Prostate, bladder, urethra, or rectal pain (rare): see notes 1,2,3. May require treatment with antibiotics, surgery (either open or cystoscopic), analgesics, or other medications placed in the bladder, urethra, or rectum.

Impotence (Less likely, but serious): see notes 1,2. May require treatment will medications (e.g. Viagra, Muse, etc...), other erectile aids (e.g. penile pump), or surgery (implantable penile prosthesis).

Reduction in ejaculate volume (likely), which could reduce fertility: This condition is highly likely following treatment since the target includes structures which contribute to semen.

Pain with ejaculation, or change in the sensation of orgasm (less likely): see note 2,3. May require analgesics.

Rectal or urethral ulceration, or fistula, which could result in colostomy and/or ileostomy (rare, but serious): see notes 1,2,3. Could also require antibiotics, suprapubic or Foley catheter, liquid diet, hypobaric oxygen treatments, medications or other surgeries.

Reproductive Risks: No fertility issues pertinent to this patient population

Note 1: because the CyberKnife® treats the prostate with over 100 beams coming from many directions, radiation dose is concentrated on the prostate. Compared with other external beam radiation devices, less radiation dose is given to the surrounding normal tissues, such as the rectum and bladder. In addition, throughout treatment, CyberKnife® frequently images the prostate and corrects for movement of the patient or the prostate. This allows physicians to treat a smaller region around the prostate compared to other commonly used externally generated radiation methods. This minimizes radiation exposure to surrounding normal structures. The design characteristics of the CyberKnife® thus intrinsically minimize the risk for side effects or adverse effects.

Note 2: the radiation tolerance of the normal tissues surrounding the target has been carefully considered, and likely acceptable tolerances have been calculated. These normal tissue constraints are listed in section 8.3.2. DVH analyses will be performed as specified, to insure adherence to these constraints, thus minimizing risk.

Note 3: the large dose per fraction delivered with CyberKnife® takes advantage of the low α/β ratio of prostate cancer relative to the surrounding normal structures. The hypofractionation scheme this reduces the risk of side effects or adverse effects.

12.2. Risks Associated with Fiducial Placement:

Infection (rare): In the event that a patient experiences infection as a result of fiducial placement, antibiotic treatment will be prescribed.

12.2 Minimization of Risk:

Stringent inclusion/exclusion criteria have been incorporated into this protocol to assure that any subject who may be at increased risk from an adverse event is not enrolled into this clinical study. Subjects will be observed post procedure to assure that any acute adverse effects are detected in a timely manner so that proper medical treatment can be initiated. Subjects also will be provided with instructions as to whom to contact along with contact telephone numbers, in the event they experience any complications.

12.3 Potential Benefits:

Although previously confined to intracranial treatment, SRS is gaining recognition in the medical community as an alternative to external beam radiation therapy in other parts of the body. Use of the CyberKnife® system may provide the following benefits:

- Minimally invasive procedure performed on an outpatient basis
- Lengthen interval to tumor progression
- Improved survival
- Decreased genitourinary, rectal and gastrointestinal toxicities compared with conventional radiation therapy and radical prostatectomy
- Decreased toxicities to sexual function compared to other types of radiation therapy and radical prostatectomy

12.4 Early Termination:

Subjects may withdraw or be discontinued by the investigator from the clinical evaluation at any time; however, they may be requested to continue with their follow-up PSA tests and exams five years following their last SRS treatment.

